4.5. Recruitment, eligibility, exclusion criteria, consent, and follow-up procedures

4.5.1 Treatment recruitment

In order to encourage high treatment coverage in the community-wide intervention arm, community sensitization activities will take place within one month of scheduled MDA events. Sensitization activities will be designed in close consultation and collaboration with the National NTD programme and in accordance with site norms and past MDA experiences. Where possible, MDA activities will be scheduled to accommodate seasonal and cultural activities that might influence MDA participation, such as holidays, migratory events, or crop harvesting.

4.5.2 Treatment eligibility

In intervention clusters, all individuals 24 months of age and older and not in their first trimester of pregnancy will be eligible for treatment with albendazole, in accordance with WHO guidelines. In targeted MDA clusters, all pre-SAC and SAC 24 months of age and older will be eligible for treatment.

4.5.3 Study eligibility and enrollment

The population eligible for sampling in the intervention and control arms include all individuals 12 months of age or older who are confirmed by study staff as residing within the study clusters.

During the cross-sectional surveys, participants will be approached and asked to provide fecal samples. If participants are unable or unwilling to produce whole stool, a self-administered rectal swab will be offered and instructions for fecal collection provided. Fecal collection kits will be collected within 24 hours of the sample being produced.

In the longitudinal monitoring cohort, participants will be enrolled in conjunction with the baseline cross-sectional surveys, prior to the first round of MDA. Fecal collection kits will be dispersed to each participant at the time of enrollment and annually thereafter, coinciding with planned MDA activities.

4.5.4 Treatment exclusion criteria

Populations excluded from treatment include children under 24 months of age and pregnant women in their first trimester.

4.5.5 Study exclusion criteria

Survey (cross-sectional and longitudinal) exclusion criteria include: individuals who cannot be confirmed as living in the study clusters, who do not provide informed consent, or for children 7 years and above who refuse assent. Additionally, participants will be excluded from the longitudinal monitoring cohorts if they report that they plan to move out of the study area within the study period.

4.5.6 Consent

The head of household or other adult member of the household will give written informed consent for participation in the census, or will provide a thumbprint if unable to write. Participants in each round of cross-sectional sampling will give written informed consent for their participation or will provide a thumbprint if unable to write. Participants in the longitudinal monitoring cohorts will provide consent for repeated sample collection and repeated rounds of data collection at enrollment. If a child is selected, parents or guardians will give written informed consent on behalf of the child and children aged 7 and older will provide assent.

4.5.7 Follow-up

Up to three attempts will be made to reach each household or individual for the purposes of the censuses and the cross-sectional prevalence assessments, respectively. Individuals participating in the longitudinal cohort will be asked to provide contact information and every effort will be made to ensure high rates of retention in the cohort. Contact will be attempted by phone or household visits if individuals are missed during routine follow up.

4.6 Adverse event monitoring

Adverse events will be passively monitored for all participants in the study. Reports of severe adverse events, including all deaths and any events classified as “definitely”, “probably” or “possibly” related to the study drug according to WHO criteria will be reported to the Data Safety Monitoring Committee (DSMC) and to all appropriate regulatory bodies.

4.7 Costs data collection

The DeWorm3 project will conduct cost-effectiveness evaluations following three years of MDA and then again following two years of surveillance. Financial and non-financial economic costs will be collected using standardized cost collection forms over the duration of the study. The perspectives used will be individual (i.e. participant), societal, and health systems-level (i.e. government). We will utilize WHO guidelines [15] and an ingredients-based approach to quantify the resources and associated unit costs required to deliver twice-yearly community-wide MDA and annual school-based MDA. We will organize the costs according to standard expenditure categories, including: personnel (salaries), volunteer community drug distributor time, supplies including drugs, equipment, services, space and overhead. We will also attempt to measure the time demanded by community-members to participate in different aspects of the intervention. Full incremental costs will be derived, measured in the local currency, and converted to US dollars.

4.8 Data management

The DeWorm3 coordinating team will ensure harmonization of data collection and data management processes across all sites. All sites will collect information on a core set of variables with standard definitions using digital data collection methods or, when necessary, paper-based methods. Each site will be responsible for data entry and initial cleaning of the data, including running range and consistency checks as well as periodic reviews of distributions and identification of outliers. Each study site will resolve any inconsistencies within their database in consultation with their field data collection team and with field verification if needed. DeWorm3 will provide a set of range and consistency checks that must be applied to these variables.

De-identified data will be shared with the DeWorm3 coordinating center at the Natural History Museum, London, UK and with the clinical trials support unit at the University of Washington, Seattle, USA and a harmonised central database will be maintained. The DeWorm3 data manager will run another set of range and consistency checks including checking of consistency of data quality across sites. Any inconsistencies or queries will be communicated to the study site, which

will be expected to check and address the list of queries and resubmit data. Cleaned de-identified data from all sites will be pooled and stored in a secure database at the Natural History Museum.

5. STUDY MANAGEMENT

5.1 Coordination

The Principal Investigator (PI) of the Project is assisted by two Deputy Chief Operating Officers - a Director of Finance and Operations and a Director of Science and Policy and one or more Project Managers based at the Natural History Museum in London. These Project leads will work closely with a support team internal to the Project, and are responsible for the conduct and output of the project, and for communication with the Bill & Melinda Gates Foundation. Each site will appoint a PI responsible for ensuring the agreed protocol is comprehensively and precisely implemented at the respective site according to the agreed time frame. The site PI will represent the interests of the respective site partners in communication with the Project leads and support team of the Project. The Project leads will work closely with the site PIs throughout the Project to ensure the interests, views and priorities of all sites are taken into consideration. The DeWorm3 coordinating team at the Natural History Museum is supported by three units;

- Clinical Trial and Implementation Science Support Unit, University of Washington, USA
- Modeling and Trial Simulation Support Unit, Imperial College London
- Economic Analysis Support Unit, Swiss Tropical and Public Health Institute

These support units may receive copies of data from the trial sites to conduct associated modeling and data quality assurance activities.

5.2 Advisory Groups

A **community advisory board (CAB)** will be established at each study site and designed in accordance with site preferences in order to guide and inform appropriate implementation of all study procedures and engagement with community members.

A Programme Partnership and Advisory Committee (PPAC) consisting of funding partners and leadership at the Natural History Museum as the DeWorm3 primary grantee institution will provide support to Project leadership on major Project decisions. A Strategic Advisory Committee will provide external advice on overall strategic decisions and will support advocacy for the Project internationally. Subject matter experts will form a Technical Advisory Board to provide technical expertise on specific aspects of the Project. The Project leadership will be responsible for inviting the members of the respective committees, and site PIs will suggest relevant local experts for consideration as Advisory Group members.

5.3. Data Safety Monitoring Board Review

Per standard practice, MDA programs distributing albendazole conduct passive adverse event (AE) monitoring and reporting. In addition, DeWorm3 will form a Data Safety and Monitoring Committee (DSMC) prior to study initiation to monitor severe adverse events (SAEs) and to evaluate the statistical analysis plan. The DSMC membership will include expertise in clinical trials, statistics, STH infections, and ethics in resource limited settings. SAEs will be reported to the DSMC and all relevant IRBs within 48 hours of the study team becoming aware of such events and will be summarized and reported to study investigators and relevant institutional review boards on a twice-yearly basis.

5.4 Quality Assurance

Field supervisors will check all forms completed by field workers before data entry or upon data upload. Data cleaning quality assurance will be performed using standard operating procedures, and consistency and range checks both at the study sites and centrally at the Natural History

Museum and/or the University of Washington. Data quality checks will also be applied on a quarterly basis and feedback will be provided to the PIs and study managers in all sites. PIs will provide brief monthly progress reports during the entire study period and will participate in regular telephone conferences with DeWorm3 staff. The monthly progress reports will include details regarding preparations for future MDA, MDA treatment coverage, drug supply chain management, workforce training and management, and interim laboratory findings.

6. LABORATORY PROCEDURES AND SPECIMEN COLLECTION AND STORAGE

6.1 Specimen collection

Consenting participants will be provided plastic containers for collection of a fresh morning/first stool sample, to be submitted within 24 hours of the time it is collected. Stool will be collected from households or, if necessary, delivered to a central location, depending on participant preference. Rectal swabs may be collected in circumstances where individuals are not able to provide stool samples. Instructions for rectal swab self-collection (or caregiver collection for children) will be provided at the time of stool collection.

Participants in the longitudinal cohort will have finger prick blood samples taken at the final round of follow-up to contribute whole blood, stored as dried blood spots, and a subsample will provide urine and saliva samples as well.

6.2 Specimen analysis

Stool samples will be divided into aliquots for microscopic examination, DNA extraction, and storage. Each unit will be labeled with barcoded patient ID codes.

Aliquots containing a minimum of 2g of stool and/or rectal swabs collected during the cross sectional surveys and longitudinal monitoring surveys will be stored for parasite DNA extraction, enteric pathogen detection, enteric function and qPCR analysis, in order to understand factors associated with helminth clearance or persistence. Stool samples or extracted DNA may be pooled to improve efficiency of testing.

All sites will ship duplicates of 10% of all study samples to the central laboratory facility at Christian Medical College (CMC) in Vellore, India for quality assurance and control. CMC will ship 10% of their samples collected to Smith College, Massachusetts, USA for quality assurance and control. Where standardization of assays is required or where technical limitations affect the ability to complete testing in a timely manner using methods described by Williams et al. [13]), stool samples or extracted DNA from stool will be shipped to central laboratory facilities at the Natural History Museum, the National Institutes of Health, CMC, the University of Washington or Smith College.

A subset of samples will be analysed in duplicate by microscopy (Kato-Katz) to facilitate rapid assessment of cluster-level prevalence, to identify prevalence trajectories, and to provide treatment to those still in need post-MDA. Aliquots of stool will be analysed within 24 hours of collection and within 30 minutes of sample preparation, to prevent the degradation of hookworm eggs. Two slides will be prepared and analysed per specimen. Ten percent of slides will be submitted for quality control checks to be performed by laboratory supervisors. Laboratory personnel will be blinded to treatment allocation during assessment.

At least three dried blood spots will be collected on filter paper and stored using appropriate application of stacking, desiccant packets, and humidity cards [16].

Urine will be collected and frozen from a subset of participants during coverage validation surveys. These specimens will be sent to Laboratorio de Farmacología CIVETAN (Argentina) or the Natural History Museum, London and analysed using HPLC or rapid chromatographic immunoassays for the detection of albendazole metabolites.

6.3 Specimen storage

Stool samples intended for DNA extraction and stored for subsequent analyses will be cryopreserved at -80°C. Parasite material identified within stool samples will be isolated and stored at each respective site for future molecular testing for drug resistance and parasite diversity analysis. Parasite material will be shipped to the central parasite repository at the Natural History Museum, London.

Dry blood spot cards will be transported to refrigerators within 7–10 days of collection and stored at -20°C [16]. Where feasible, haemoglobin measurements made be conducted using whole blood on site. Along with stored stool and rectal swabs, one of the three cards will be held in DeWorm3 processing areas at the Natural History Museum in London. Future applications to relevant ethical review committees may be made for the purposes of other unspecified analyses.

7. STATISTICAL ANALYSIS PLAN

All analyses will be conducted separately for each site, unless otherwise specified.

Primary objectives

The effect of the primary exposure on endline infection with the predominant STH species driving transmission in each site (Objective 2.1.1) will be analysed using generalized estimating equations with binomial family and exchangeable correlation matrix. The primary exposure variable will be randomisation arm, while the primary outcome will be individual-level STH infection status (positive or negative for the dominant species driving transmission species by qPCR). Models may be adjusted for baseline cluster-level STH prevalence and urban/rural designation, socioeconomic status (SES), water sanitation and hygiene (WASH) access, age, gender of the participant, household size, or other relevant variables as appropriate. In the primary analysis, these data will be analysed separately by site, while a secondary analysis will pool all data and test for effect modification using an interaction term between study site and randomisation arm.

Transmission interruption in a cluster (Objective 2.1.2) will be defined as achieving a cluster prevalence $\leq 2\%$ of the dominant STH species driving transmission at each site by qPCR 24 months after the final round of MDA. The effect of the primary exposure on the proportion of clusters in which transmission is successfully interrupted will be calculated by comparing the proportion of clusters in each arm in which transmission is successfully interrupted using a chi-squared test.

Secondary objectives

The effect of randomisation arm on endline infection with each individual species of STH (2.2.1), on the proportion of clusters interrupting transmission of each individual species (2.2.2), on endline infection with any STH species among children (2.2.2) and on shedding of fertilized *Ascaris* eggs (2.2.3) will be analysed using generalized estimating equations with binomial family and exchangeable correlation matrix or chi-squared tests, as detailed above. Models may be adjusted for baseline cluster-level STH prevalence and urban/rural designation, SES, WASH access, age, gender of the participant, household size, or other relevant variables as appropriate.

Secondary analyses

The influence of MDA strategy on treatment coverage of Pre-SAC and SAC will be analysed using self-reported coverage (defined as receiving and taking albendazole during the last round of MDA) from coverage validation surveys in each arm. The effect of randomisation arm on self-reported coverage will be analysed using generalized estimating equations with binomial family and exchangeable correlation matrix and may be adjusted for child's age, gender, current school attendance, and study year or other relevant variables as appropriate.

Cluster-level correlates of STH transmission interruption (as defined by reaching a cluster prevalence of any STH $\leq 2\%$ 24 months after stopping MDA) will be assessed using logistic regression. Key correlates of breaking the transmission of STH will include baseline prevalence and species-specific distribution of STH infection, age distribution, population migration levels, treatment coverage and compliance, rates of open defecation and population density.

The incremental cost-effectiveness ratios (ICERs) of community-wide MDA compared to the standard of care (targeted MDA) will be measured using outcome metrics such as the cost per person treated, the cost per percent reduction from baseline to endline prevalence, and the cost per incident case avoided as determined through mathematical models informed by cluster-level prevalence and intensity data. We will utilize both a short-term time horizon of the study duration as well as longer-term time horizons with extrapolations of 5, 10, and 15 years. Costs will be discounted at 3% per year and sources of uncertainty will be explored in univariate and probabilistic sensitivity analyses [14, 15].

8.1 Sample size calculations for Primary Objectives

Primary Objective 2.1.1

To compare the prevalence of the predominant STH species driving transmission at a particular study site (*most frequently A. duodenale or N. americanus*) measured by quantitative PCR 24 months after stopping MDA between clusters randomised to receive twice-yearly community-wide MDA versus clusters randomised to receive standard of care pre-SAC and SAC targeted MDA.

Power calculations for a range of scenarios were conducted. The following formula outlined by Hayes and Moulton [16]:

$$c = 1 + (Z_{\alpha/2} + Z_{\beta})^2 \frac{[\pi_0(1 - \pi_0) + \pi_1(1 - \pi_1)][1 + (m - 1)\rho]}{m(\pi_0 - \pi_1)^2}$$

was used to calculate the prevalence in the control clusters (π_0) that would enable detection of a difference between arms with 80% power, given an endline prevalence in the intervention clusters (π_1) of 2% and a range of assumptions of intracluster correlation coefficient ($\rho = 0.003$ to $\rho = 0.005$), number of clusters per arm ($c = 15$ to $c = 20$) and number of people sampled per cluster ($m = 500$ or $m = 1,000$), assuming $\alpha=0.05$. The detectable alternative π_0 ranged from 3% to 3.5%.

Power to detect differences in final prevalence between arms given plausible values for π_0 , ranging from 7% to 10% (comparable to pre-intervention prevalences in each of the study sites), was then estimated using simulations conducted in R. Each simulation assumed 1,000 individuals per cluster and a binomial distribution of STH prevalence with a mean of 2% in the intervention clusters and π_0 in the targeted arm, a range of ICC and $\alpha=0.05$; 10,000 repetitions were run for each scenario. Power was $\geq 98\%$ for all scenarios simulated.

Primary objective 2.1.2

To determine whether the transmission of the predominant STH species driving transmission at a particular study site (most frequently *A. duodenale* or *N. americanus*) can be interrupted using MDA with albendazole, defined as reaching a combined point prevalence of $\leq 2\%$ of that species measured by quantitative PCR 24 months after stopping MDA in clusters receiving either twice-yearly community-wide MDA or standard of care pre-SAC and SAC targeted MDA.

Power to detect transmission interruption and differences by arm was also estimated using simulation in R. The threshold for transmission interruption was set at 2.0% prevalence, and a cluster was considered to have interrupted transmission if prevalence could be declared to be below the threshold with 95% confidence, using a one-sided binomial test. Simulations estimated power to a) declare elimination in 50% of intervention clusters, which was selected as the minimum proportion of intervention clusters that would need to achieve elimination in order for the intervention to be recommended for scaleup, and b) detect a difference in the proportion of clusters in which transmission was interrupted by arm.

Simulations assumed 20 clusters per arm, 500 or 1,000 individuals per cluster (m), and a binomial distribution of STH prevalence with a mean of 7% in the targeted arm (π_0) and π_1 in the intervention arm, a range of ICC ($\rho = 0.003$ or $\rho = 0.005$), and $\alpha=0.05$; 10,000 repetitions were run for each scenario.

a) The power to declare elimination in 50% of the intervention clusters varies with the mean endline prevalence, the ICC, and the number sampled per cluster as shown in Figure 7.

[figure not shown]

Figure 7: Power to declare elimination in 50% of intervention clusters (Primary Objective 2.1.2) by intracluster correlation (ICC) and number of people estimated per cluster(m) estimated by simulation.

b) For a fixed mean endline prevalence of 7% in the targeted arm (π_0), power to detect a difference in the proportion of clusters eliminated varies by number of individuals sampled per cluster, ICC and endline prevalence in the intervention arm (π_1), as shown in Figure 8.

[figure not shown]

Figure 8: Power to detect a difference in the proportion of clusters achieving transmission interruption (Primary Objective 2.1.2) assuming 7% mean prevalence in the targeted

clusters (π_0), by mean endline prevalence in the intervention clusters (π_1), intracluster correlation (ICC) and number of people measured per cluster (m), estimated by simulation.

These power calculations demonstrate that with 20 clusters per arm, measuring STH infection among 500-1,000 people per cluster at endline will provide adequate power for the primary objectives in most scenarios. Sample size estimates may be refined using data on intra-cluster correlation and baseline prevalence at each site collected during the study.

Prevalence estimates by Kato-Katz

Stool samples collected from longitudinal monitoring cohorts annually will be analysed with Kato-Katz techniques as well as being stored for analysis by qPCR.

Assuming 150 individuals sampled per cluster, 20 clusters per arm, and using Kato-Katz sensitivity of 0.65 and specificity of 0.94 [17], to estimate true prevalence; using Blaker's CI for imperfect diagnostic tests [18] to estimate 95% CI by cluster; and adjusting for design effect with $ICC=0.003$ to estimate 95% CI by arm, the precision of prevalence estimates by true prevalence are summarized in Table 1.

Table 2. Precision of prevalence estimates by Kato-Katz.

Observed prevalence by Kato-Katz	True prevalence	95% CI by cluster	95% CI by arm (across 20 clusters)
14.9%	15%	6.1-25.7%	12.5-17.6%
11.9%	10%	2.0-19.4%	7.7-12.5%
9.0%	5%	0.0-13.6%	3.0-7.2%
7.2%	2%	0.0-9.8%	0.2-3.9%

The prevalence estimate from the first assessment of the longitudinal monitoring cohort will provide baseline prevalence information for clusters prior to randomization. At endline, however, the longitudinal monitoring cohort's testing and treatment history may differ from that of the general population of the clusters. For this reason, a subset of samples collected as part of the cross-sectional sample after the final round of MDA will also be analysed using Kato-Katz.

Coverage estimation by urine albendazole

The primary assessment of coverage will be by self-report. However, a small number of participants in the coverage survey approached between 24-72 hours after MDA will be asked to provide a urine sample to be assessed for albendazole metabolites. Results of the urine analysis will be used to validate self-reported true coverage of MDA, i.e. the proportion of individuals who both received and swallowed pills during MDA. The assay is still being validated and sensitivity / specificity information to be determined. Precision of estimates of true coverage across a range of assay sensitivities, with an assumed specificity of 99%, are shown in Table 3.

Table 3. Precision of estimates of true MDA coverage by urine albendazole.

True coverage	Sensitivity	95% CI of coverage assessment	
		n=100	n=150
95%	95%	87-100%	89-99%

	85%	84-100%	86-100%
	75%	82-100%	84-100%
90%	95%	81-96%	83-95%
	85%	79-99%	81-97%
	75%	76-100%	79-99%
80%	95%	70-88%	72-87%
	85%	68-90%	70-88%
	75%	66-93%	69-90%

Assuming true coverage of 90% or higher and a minimum sensitivity of 85%, assessment of 150 individuals per site will provide adequate power to rule out coverage <80%.

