To ensure high coverage and compliance, a random sample of 50 households in all clusters will be invited to participate in a **post-MDA coverage survey** within one week of receiving MDA, prior to any cluster-wide mop-up activities. All individuals in the selected household will be invited to participate in the coverage survey. This survey will be conducted in all clusters, in both study arms. The purpose of the survey is to collect critical information regarding validated treatment coverage. Treatment coverage is defined as the proportion of eligible individuals who ingested albendazole during MDA. The number of eligible individuals will be ascertained during each annual census. This will provide important information regarding the benefits of different delivery systems in maximizing treatment coverage. Individuals in randomly selected households will be asked if they participated in the MDA event and, if not, their reason for not participating. Questions in the survey will align with WHO-endorsed coverage survey for use by national programmes. In accordance with the same NTD coverage survey guidelines, the individuals who conduct the coverage survey in a given cluster will not be the same individuals who delivered the drugs [12].

Additionally, up to 250 urine samples per site will be collected from a subset of individuals in the post-MDA sentinel survey and stored for future measurement of albendazole metabolites to confirm compliance with MDA.

An annual **school facility survey** will also be conducted to assess the presence of water and sanitation facilities at schools in all clusters and to validate coverage of MDA delivered to SAC. At baseline, a comprehensive survey will be administered with confirmation of the facilities listed. Subsequent surveys will be designed as short updates to confirm the status of water and sanitation facilities, record any changes, and review and abstract data from school records regarding treatment coverage as an opportunity to validate post-MDA sentinel survey data.

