### 4.2 ADHERENCE AND PROTOCOL DEVIATIONS

Adherence to the protocol is measured at both the cluster and individual levels. Adherence at the cluster-level refers to rounds of community-wide MDA in the intervention arm, reaching all communities in intervention clusters, being conducted according to the trial schedule laid out by each site.

Individual-level adherence refers to coverage, reach and uptake of MDA among the targeted population: school-age and preschool-age children in the standard of care arm and all age groups eligible in the intervention arm (Table 1). Coverage, reach and uptake are measured using individual treatment logs based on the most recent census in the intervention arm, and using self-report on coverage surveys in both arms (Figure 2).

Each round of MDA in the intervention arm has a target coverage and uptake of 80% of eligible study participants.

Protocol deviations, including missed or rescheduled rounds of MDA and reassignment of households or communities from one cluster to another, are documented in a Protocol Deviations Log and reviewed twice annually during DeWorm3 Data Safety and Monitoring Committee (DSMC) meetings.

Per protocol coverage Treatment logs	Directly observed Tx Treatment logs	Treatment uptake Treatment logs	Self-reported coverage Coverage Survey
Number of censused, eligible cluster residents treated Number of censused, eligible cluster residents	Number of censused, eligible cluster residents directly observed taking treatment Number of censused, eligible cluster residents not recently treated	Number of censused, eligible cluster residents treated Number of censused, eligible cluster residents reached during MDA	Number of surveyed individuals reporting swallowing a tablet Number of surveyed individuals
Population coverage Treatment logs	Non-migratory coverage Treatment logs	Pediatric coverage Treatment logs	
Number of individuals treated Number of censused, eligible cluster residents + those newly encountered during MDA	Number of censused, eligible non-migratory individuals treated Number of censused, eligible non-migratory cluster residents	Number of censused, eligible children treated Number of censused, eligible resident children	

Figure 2: Treatment coverage definitions employed in DeWorm3.

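### At the protocol's own minimum assumptions, 150 urine samples per site give about 61–68% power to rule out coverage below 80%, so the claim of adequate power is not supported there

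*Protocol*

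**What the plan says.** The last part of Protocol section 8.1 plans a urine assay for albendazole metabolites to validate self-reported swallowing of tablets. Table 3 is introduced as "Precision of estimates of true coverage across a range of assay sensitivities, with an assumed specificity of 99" per cent, and gives 95% intervals for n=100 and n=150. At 90% coverage, 85% sensitivity and n=150, the interval is 81–97%.

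The sentence after the table opens with "Assuming true coverage of 90% or higher and a minimum sensitivity of 85" per cent and concludes that "assessment of 150 individuals per site will provide adequate power to rule out coverage <80" per cent. It does not say what power is meant, at what significance level, or by what test.

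Four other places bear on it:
- The same subsection says "The primary assessment of coverage will be by self-report".
- For Primary Objective 2.1.1, section 8.1 solves for the control prevalence that "would enable detection of a difference between arms with 80% power".
- For Primary Objective 2.1.2, a cluster counts as having interrupted transmission if its prevalence can be "declared to be below the threshold with 95% confidence, using a one-sided binomial test".
- Section 4.4 allows that "up to 250 urine samples per site will be collected from a subset of individuals in the post-MDA sentinel survey".

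**The concern.** A power claim made for a whole range has to hold at the bottom of that range. The only support offered is Table 3, whose interval at the minimum values just excludes 80%. That interval is the one obtained when the observed count equals its expectation. About half of all samples fall below expectation, so an interval that only just clears the threshold at the expected count implies power not far above one half.

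At stake is how a urine result is read. A site with true coverage of 90% and a test of 85% sensitivity could fail to exclude 80% fairly often by chance, and the protocol tells its readers not to expect that.

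**Working it through.** **Inputs (all Protocol section 8.1).** Coverage under the alternative 90%; coverage to be ruled out 80%; sensitivity 85%; specificity 99%; n=150. The 80% power benchmark is taken from Primary Objective 2.1.1, because the urine sentence gives none.

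**Expected proportion testing positive** = coverage × sensitivity + (1 − coverage) × (1 − specificity).
- At 80% coverage: 0.80 × 0.85 + 0.20 × 0.01 = 0.682.
- At 90% coverage: 0.90 × 0.85 + 0.10 × 0.01 = 0.766.
- Expected positives at 90%: 150 × 0.766 = 114.9, so 115.

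**Reproducing Table 3.** Limits for 115/150 are converted to coverage by (limit − 0.01)/(0.85 + 0.99 − 1) = (limit − 0.01)/0.84. Blaker's method, which the protocol names for Kato-Katz and is assumed here for urine, gives 81.1–97.5%. Wilson limits give 81.3–97.3%. The protocol prints 81–97%, so the table is right.

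**Power.** X is the number of positives among 150. Coverage below 80% is ruled out when X reaches the cut-off k. Exact binomial results:

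| k | P(X ≥ k) at 80% coverage | Power: P(X ≥ k) at 90% coverage | Rule giving this cut-off |
|---|---|---|---|
| 114 | 0.023 | 61.2% | two-sided 95% (exact, Blaker, Wilson, mid-p) |
| 113 | 0.035 | 68.3% | exact one-sided 5% (also two-sided Wald) |
| 112 | 0.051 (mid-p 0.043) | 74.7% | mid-p, Wilson, Blaker or Wald, one-sided 5% |
| 111 | 0.073 | 80.3% | no 5% rule examined |

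The expected count of 115 is only one above the two-sided cut-off of 114.

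**Normal approximation.** The difference is 0.766 − 0.682 = 0.084. The standard errors are √(0.682 × 0.318/150) = 0.0380 at 80% coverage and √(0.766 × 0.234/150) = 0.0346 at 90%. One-sided 5%:
- Null variance: Φ[(0.084 − 1.645 × 0.0380)/0.0346] = 73.3%.
- Alternative variance: Φ[(0.084 − 1.645 × 0.0346)/0.0346] = 78.4%.

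The two-sided counterparts are 60.8% and 68.1%. No rule examined that works at the 5% level reaches 80%.

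**Elsewhere in the stated range (n=150, exact).**

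| Coverage | Sensitivity | Two-sided 95% | One-sided 5% |
|---|---|---|---|
| 90% | 90% | 68% | 81% |
| 90% | 95% | 82% | 87% |
| 92% | 85% | 78% | 84% |
| 93% | 85% | 85% | 89% |
| 95% | 85% | 94% | 96% |

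At 85% sensitivity, power reaches 80% from true coverage of 92.2% (two-sided 95%), 91.5% (exact one-sided 5%) or 90.7% (mid-p one-sided 5%).

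**Larger samples at 90% coverage and 85% sensitivity.** Exact power is saw-toothed in n. Two-sided, it first reaches 80% at n=227, drops back (79.3% at n=236), and stays at or above 80% from n=241; it is 82% at n=250. Exact one-sided 5% power stays at or above 80% from n=196 and is 91% at n=250.

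**The case against.** The strongest reply is that the sentence never defines adequate, so the 80% benchmark is imported from a primary objective, and power may be loose wording for the precision in Table 3. It is true that no printed number is contradicted. But the sentence uses the word power without qualification, and failing to exclude 80% in 32% (exact one-sided) to 39% (two-sided) of samples is hard to call adequate.

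A second reply is that ruling out low coverage is a one-sided question, and that the protocol's own threshold rule for Objective 2.1.2 is one-sided. That is fair, and it makes 68% at least as natural a figure as 61%. It does not remove the shortfall.

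A third is that the gap is local and the measure ancillary. Both parts stand. The claim holds over most of the stated range. Self-report is the primary coverage measure, and SAP section 4.2 measures coverage by treatment logs in the intervention arm "and using self-report on coverage surveys in both arms", with no urine analysis or test against 80% described.

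A reader might infer more: that Table 3 is wrong, that 150 samples are too few in general, that the 150 contradicts the 250 in section 4.4, or that the trial's main conclusions are at risk. The documents support none of these. Table 3 reproduces, power is ample at more favourable values, 250 is a ceiling that 150 respects, and no primary objective uses the urine result.

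**Conclusion.** The claim of adequate power is not supported at the minimum values to which the protocol ties it. Power there is 68% (exact one-sided 5%) or 61% (two-sided 95%), and 73–78% under mid-p or normal-approximation one-sided 5% rules. The only cut-off that gives 80% carries a one-sided type I error of 7.3%. Severity is low.

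The conclusion rests on 80% as the benchmark. The figures also treat sensitivity and specificity as known and observations as independent. Section 8.1 says that the assay is still being validated, and section 4.4 invites every member of each sampled household to the coverage survey. Both probably make actual power lower than shown, by an amount the documents do not allow one to calculate.

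**What to change.** Reword the one sentence after Table 3:
- Replace the claim of adequate power with the power at 90% coverage and 85% sensitivity, naming the rule: 68% (exact one-sided 5%) or 61% (two-sided 95%) with 150 samples.
- Add that at 85% sensitivity, 150 samples reach 80% power only from true coverage of about 91.5% (exact one-sided 5%) or 92.2% (two-sided 95%).
- State that these figures take assay accuracy as known and observations as independent, so actual power is probably lower given household sampling.

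This costs protocol wording only. Optionally, reconcile the 150 with the ceiling in section 4.4. At the minimum assumptions, 80% power is held from 196 assays (exact one-sided 5%) or 241 (two-sided 95%). That is 46 or 91 more per site than the 150 planned, and within the 250 already allowed.
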